8.4.2 UNANTICIPATED PROBLEM REPORTING

The investigator will report unanticipated problems (UPs) to the reviewing Institutional Review Board (IRB) and to the Sponsor/CRO. The UP report will include the following information:

- Protocol identifying information: protocol title and number, PI's name, and the IRB project number;
- A detailed description of the event, incident, experience, or outcome;
- An explanation of the basis for determining that the event, incident, experience, or outcome represents an UP;
- A description of any changes to the protocol or other corrective actions that have been taken or are proposed in response to the UP.

To satisfy the requirement for prompt reporting, UPs will be reported using the following timeline:

- UPs that are serious adverse events (SAEs) will be reported according to the timelines noted in section 8.3.6.
- Any other UP will be reported to the IRB (per IRB policy) and to the CRO/study sponsor within a reasonable time period of the investigator becoming aware of the problem.

- All UPs should be reported to appropriate institutional officials (as required by an institution's written reporting procedures), the supporting agency head (or designee), and the Office for Human Research Protections (OHRP) as applicable, within the appropriate timeline (per institution policy) of the IRB's receipt of the report of the problem from the investigator.

[figure not shown]
8.4.3 REPORTING UNANTICIPATED PROBLEMS TO PARTICIPANTS

If an unanticipated problem results in a change to the informed consent form, all study participants will be provided with the updated information and re-consented with the new form.

[figure not shown]
8.5 DRUG INDUCED LIVER INJURY PLAN

If patient reports symptoms compatible with DILI (early and nonspecific symptoms include anorexia, nausea, fatigue, right upper abdominal discomfort, vomiting), liver enzyme measurements should be made immediately, regardless of when the next visit or monitoring interval is scheduled.

As part of the study screening and monitoring criteria, liver enzymes are assessed at screening, Day 7 (Study Visit 3) and Day 14 (Study Visit 5). Finding of the following will require further follow up:

If symptoms persist or repeat testing shows AT >3xULN for subjects with normal baseline measures or 2-fold increases above baseline values for subjects with elevated values before drug exposure, it is appropriate to initiate close observation to determine whether the abnormalities are improving or worsening as follows:

- Obtaining a more detailed history of symptoms and prior or concurrent diseases.
- Obtaining a history of concomitant drug use (including non-prescription medications and herbal and dietary supplement preparations), alcohol use, recreational drug use, and special diets.
- Ruling out acute viral hepatitis types A, B, C, D, and E; autoimmune or alcoholic hepatitis; NASH (Non-alcoholic steatohepatitis); hypoxic/ischemic hepatopathy; and biliary tract disease.
- Obtaining a history of exposure to environmental chemical agents.
- Obtaining additional tests to evaluate liver function, as appropriate (e.g., INR, direct bilirubin).
- Considering gastroenterology or hepatology consultations

Discontinuation of treatment will be considered if:

- ALT or AST $>8\times$ ULN
- ALT or AST $>5\times$ ULN for more than 2 weeks
- ALT or AST $>3\times$ ULN and (TBL $>2\times$ ULN or INR >1.5)
- ALT or AST $>3\times$ ULN with the appearance of fatigue, nausea, vomiting, right upper quadrant pain or tenderness, fever, rash, and/or eosinophilia ($>5\%$)

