1 PROTOCOL SUMMARY

1.1 SYNOPSIS

Title:	A Randomized, Double-Blind, Placebo-Controlled Study to Evaluate the Safety and Efficacy of TQ Formula in Treating Participants who have Tested Positive for Novel Coronavirus 2019 (BOSS-Covid-19)
Study Description:	
This is a randomized (1:1), double-blind, placebo-controlled phase 2 study to assess safety and efficacy of Total 3 g daily dose of Black Seed Oil ('TQ Formula ' this point forward) capsules versus placebo in treating patients who have tested positive for novel Coronavirus 2019 (Covid-19) in the outpatient setting.
 
Patients will be treated at a dose of 500 mg, 3 capsules, two times a day for 14 days from date of randomization.
 
Quantitative viral load as measured by RT-PCR will be evaluated at baseline and on days 7 and 14. Covid-19 symptoms will be measured throughout the study using Modified FLU-PRO Plus.
 
A detailed schematic describing all visits and a schedule of assessments is included in the Schema and Schedule of Activities, Sections 1.2 and 1.3, respectively.

Objectives:	
Primary Objective:
 
To evaluate if treatment with 3 g TQ Formula (500 mg per capsule, 3 capsules BID) given orally on outpatient basis can significantly reduce median time to sustained clinical response compared to placebo in participants with COVID-19 infection treated in the outpatient setting. Sustained clinical response is defined as a reduction of scores to </= 2 on all symptoms of the Modified FLUPRO Plus.
 
Secondary Objectives:
 
 1. To compare the viral load profile over time (from baseline through to Day 14) between treatment with 3 g TQ Formula (500 mg per capsule, 3 capsules BID) given orally on outpatient basis and placebo in participants with COVID-19 infection treated in the outpatient setting 2. To compare the percentage of RT-PCR negative/undetectable (i.e., viral clearance) on Day 7 and Day 14 in participants taking 3 g TQ Formula (500 mg per capsule, 3 capsules BID) versus participants taking placebo 3. To compare the duration and severity of symptoms (measured by

[figure not shown]
Modified FLU-PRO Plus) over time from Day 1 through Day 14 in

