6.1.2 DOSING AND ADMINISTRATION

All study participants will receive the same dose of either TQ Formula (total dosing of 3 g per day) or placebo for the duration of the study. Study participants should take 3 capsules orally (500 mg each), approximately 12 hours apart, two times per day (BID). Each dose should be taken preferably with food. Missed doses will not be made up; however, the window for dosing is +/- 6 hours. If longer than 6 hours since missed dose, participants should continue with next scheduled dose. There are no dose limiting effects anticipated with this investigational drug.

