6.2.2 FORMULATION, APPEARANCE, PACKAGING, AND LABELING

The investigational drug consists of 500 mg of black seed oil per capsule. Placebo consists of similar oil without active ingredient. Investigational drug will be undistinguishable from placebo; the appearance of the capsules and all packaging will be identical. Investigational product will be packaged as 500 mg/placebo capsules; each participant will receive a total of 84 capsules in order to take 6 capsules per day for the 14-day study treatment period. Investigational product will be labelled per CFR regulations.

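### In Protocol 8.5, the criterion of ALT or AST above 5x ULN for over two weeks cannot be met within the 14-day course, and the entry limits admit a narrow group who already meet the third criterion

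*Protocol*

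**What the plan says.** Protocol 8.5 introduces its list with "Discontinuation of treatment will be considered if". The four criteria for ALT or AST are:

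1. above 8x ULN;
2. above 5x "ULN for more than 2 weeks";
3. above 3x ULN together with total bilirubin above 2x "ULN or INR >1.5";
4. above 3x ULN "with the appearance of fatigue, nausea, vomiting, right upper quadrant pain or tenderness, fever, rash", or with eosinophilia.

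Only the first two rest on enzymes alone. Scheduled liver tests are at screening, Day 7 and Day 14. Extra tests are required at once if symptoms suggest liver injury.

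On the length of treatment, the synopsis has capsules taken "two times a day for 14 days from date of randomization". Section 6.2.2 states that "each participant will receive a total of 84 capsules in order to take 6 capsules per day for the 14-day study treatment period", and section 6.1.2 that "Missed doses will not be made up".

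On entry, exclusion 10 (Protocol 5.2, repeated in SAP 3.3.2) bars ALT or AST above 4x ULN and any laboratory value at 4x ULN or more. It has no combined enzyme and bilirubin limit. Exclusion 11 covers prior liver disease, and exclusion 15 leaves other conditions to the investigator's judgement.

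**The concern.** A stopping rule that needs more than two weeks of observation does not fit a two-week course. If it cannot be met before the last dose, it gives sites no guidance while they can still act on it. Consider a patient between 5x and 8x ULN on Day 7 with normal bilirubin and INR and none of the listed symptoms or signs. That patient meets none of the four criteria, so the list leaves the decision to the investigator without a threshold.

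The second issue concerns entry. If the eligibility limits admit someone who already satisfies a stopping criterion, that criterion reflects the entry value and not a change on drug. The site would have to consider stopping treatment that it has just started.

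**Working it through.** **Length of the course.** Supply (6.2.2): 84 capsules / 6 per day = 14 days, which reproduces the protocol's own figure. At 3 capsules per dose this is 28 doses. With 12-hour spacing, the last dose falls 27 x 12 h = 324 h = 13.5 days after the first. If the 6-hour window is stretched at both ends, 336 h = 14.0 days, which is still not more than 14. If the first dose is taken on the evening of Day 1, the last falls on the morning of Day 15.

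**Earliest day the second criterion is met.** More than 14 days, in whole days, means first documented day + 15.

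| First value above 5x ULN | Days elapsed to Day 14 | Criterion first met | Days after Day 14 |
|---|---|---|---|
| Day 1 (unscheduled test) | 13 | Day 16 | 2 |
| Day 3 (early Visit 2, if tested) | 11 | Day 18 | 4 |
| Day 6 (early Day 7 visit) | 8 | Day 21 | 7 |
| Day 7 (scheduled) | 7 | Day 22 | 8 |
| Day 8 (late Day 7 visit) | 6 | Day 23 | 9 |

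The clock cannot start at screening, because a value above 5x ULN there is excluded by the 4x limit and eligibility is checked again at baseline. Day 1 is a limiting case: the schedule in section 1.3 has no chemistry at the baseline visit unless it is combined with screening.

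**Does the toxicity hold change this?** Section 4.3 allows a delay of up to 10 days. If that delay lengthened dosing to Day 24, a Day 7 finding would reach the criterion on Day 22, inside the course. No text says that dosing is lengthened, and the synopsis counts the 14 days from randomization. If the enzyme rise itself caused a hold from Day 7 and did not recover, section 4.3 would end treatment after 10 days, on Day 17. That is 5 days before Day 22.

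**Exclusion 10 against the third criterion** (values in multiples of ULN, except INR):

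| ALT or AST | Bilirubin | INR | Meets third criterion | Barred by exclusion 10 |
|---|---|---|---|---|
| 3.5 | 2.5 | 1.0 | yes | no |
| 3.9 | 3.9 | 1.0 | yes | no |
| 3.5 | 1.0 | 1.8 | yes | no |
| 4.0 | 2.5 | 1.0 | yes | yes |
| 4.5 | 2.5 | 1.0 | yes | yes |
| 3.5 | 4.2 | 1.0 | yes | yes |

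The overlap is therefore confined to ALT or AST above 3x and below 4x ULN, with bilirubin above 2x and below 4x ULN or with INR above 1.5.

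**The case against.** The strongest reply is that section 8.5 is not the only route to stopping. Section 7.2 lets the investigator discontinue treatment for any laboratory abnormality where continuing is not in the participant's interest. It also allows this when a participant newly meets an exclusion criterion that rules out continuing. Every patient between 5x and 8x ULN has passed the 4x limit of exclusion 10. That route has a lower threshold than the 8.5 criterion and needs no waiting period. It is permissive, but so is 8.5. This reply stands, and it limits the point to the 8.5 list.

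Three stronger readings are therefore tempting but unsupported:

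- *A silent rise to 5x–8x ULN has no stopping rule anywhere.* Section 7.2 supplies one.
- *No drug can be withheld from such a patient as the plan stands.* The investigator may stop on Day 7. Given a same-day result, 84 − 42 = 42 capsules then remain.
- *The fourth criterion is also faulty because it ignores baseline.* Section 8.5 does apply a baseline rule to close observation ("2-fold increases above baseline values for subjects with elevated values before drug exposure") and not to this criterion. Someone entering above 3x ULN could meet the criterion through Covid nausea alone. Adding the doubling rule would lower protection, however. A patient rising from 2.4x to 4.7x ULN with new right upper quadrant pain meets the criterion now, but would fall below the doubled threshold of 2 x 2.4 = 4.8x. Considering a stop in that patient is a defensible, cautious choice.

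The hold in section 4.3 for drug-related adverse events of Grade 3 or above is a possible further safeguard, but its reach here is unclear. Section 8.3.5 counts a laboratory value as an adverse event only if it produces signs or symptoms and is clinically significant. Section 7.1 would report any new clinically relevant finding, and the causality definitions in 8.3.3.2 mention abnormal laboratory results.

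On entry, exclusions 11 and 15 may catch the patient by history or judgement.

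**Conclusion.** The point holds within the section 8.5 list. The two-week criterion cannot be met during the planned course, so above 8x ULN is the only enzyme-only criterion there that can act while the patient is being dosed. Exclusion 10 also leaves a narrow window in which a patient meets the third criterion before the first dose.

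The consequence is a small weakness in a safety rule. The list is advisory, section 7.2 gives earlier and broader powers, and close observation still applies. The documents give no frequency for either situation. A reader might infer some effect on the efficacy result; nothing in the documents supports that.

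The conclusion assumes that a treatment hold does not lengthen dosing, as the text stands. It also rests on the protocol text supplied. The SAP cites Protocol Version 6.0, and its exclusion list differs from the supplied protocol in other items (a kidney function limit and CYP2C9 substrates), so section 8.5 may read differently in that version. The SAP does not reproduce section 8.5.

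**What to change.** 1. **Protocol 8.5, second criterion.** Replace it with: *ALT or AST >5x ULN, confirmed on repeat testing no later than the next study visit*. State that this does not limit the investigator's power to stop earlier under section 7.2. A Day 4 value would be repeated by Day 7, and a Day 7 value by the Day 10 visit (Day 9 to 11), before dosing ends.
2. **Protocol 5.2 item 10 and the matching item in SAP 3.3.2.** Add: *or ALT/AST >3 times the ULN with total bilirubin >2 times the ULN*. INR is left out because the screening panel lists prothrombin time and not INR, so the small INR part of the overlap stays with investigator judgement.

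Leave the first, third and fourth criteria and the 4x entry limit as they are.

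The cost is wording only; no visit or assay is added. ALT, AST and bilirubin are already on the screening panel. The repeat test can use the Day 4 or Day 10 chemistry that section 1.3 allows when clinically indicated, with that telehealth visit changed to in-person, or the scheduled Day 7 and Day 14 chemistry. The downside is a few more discontinuations to consider and possibly a rare extra exclusion. As an assumption only, if 0 to 2% of otherwise eligible patients had the combined elevation, that would be 60 x 0 to 60 x 0.02 = 0 to 1.2, or about 0 to 1 of 60.

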9 STATISTICAL CONSIDERATIONS

A separate Statistical Analysis Plan will be written to describe the statistical analysis procedures addressing each primary, secondary and exploratory aims in detail.

9.1 STATISTICAL HYPOTHESES

The primary statistical hypotheses are:

1. Treatment with 3 g TQ Formula (500 mg per capsule, 3 capsules BID) given orally on outpatient basis (study drug) will significantly reduce median time to sustained clinical response compared to placebo in participants with COVID-19 infection treated in the outpatient setting. Sustained clinical response is defined as a reduction of scores to ≤ 2 on all symptoms of the Modified FLU-PRO Plus.

The secondary statistical hypotheses are as follows:

1. Study drug will significantly reduce quantitative viral load by Day-14 compared to placebo in participants with COVID-19 infection treated in the outpatient setting.
2. Study drug will significantly increase the percentage of negative/undetectable RT-PCR viral load at Day 7 and Day 14 in participants taking 3 g TQ Formula (500 mg per capsule, 3 capsules BID) versus participants taking placebo in participants with COVID-19 infection
3. Study drug will significantly reduce duration and severity of symptoms overall and within each symptom domain overtime from Day 1 to Day 14 compared to placebo in participants with COVID-19 infection
4. There is a significantly positive correlation between quantitative viral load and symptom severity at baseline, at Day 7, and Day 14 in patients with COVID-19 infection

5. Study drug will lead to acceptable AE and SAE profiles compared to placebo

- Primary Efficacy Endpoint(s):
 1. Measurement of the difference in median time to sustained clinical response in participants taking 3 g TQ Formula (500 mg per capsule, 3 capsules BID) versus participants taking placebo.
- Secondary Efficacy Endpoint(s):
 1. Measurement of change in quantitative viral load from baseline, Day 7, and Day 14 using RTPCR in participants taking 3 g TQ Formula (500 mg per capsule, 3 capsules BID) versus participants taking placebo with COVID-19 infection.
 2. Percentage of negative/undetectable RT-PCR (i.e., viral clearance) on Day-7 and Day-14 in participants taking 3 g TQ Formula (500 mg per capsule, 3 capsules BID) versus participants taking placebo
 3. Measurement of severity of and change in Covid-19 symptoms per total score as well as sub-scores (Nose, Throat, Eyes, Chest/Respiratory, Gastrointestinal, Body/Systemic, Taste/Smell) measured through Modified FLU-PRO Plus from Day 1 through Day 14 in participants with COVID-19 infection treated either with 3 g TQ Formula (500 mg per capsule, 3 capsules BID) or placebo
 4. Correlation Coefficient of quantitative viral load and symptom severity at baseline, at Day 7, and Day 14 in participants taking 3 g TQ Formula (500 mg per capsule, 3 capsules BID) versus participants taking placebo
 5. Number of overall adverse events, related adverse reactions, and hospitalizations reported in participants taking 3 g TQ Formula (500 mg per capsule, 3 capsules BID) versus participants taking placebo. All AEs/SAEs will be captured throughout the study as per schedule of assessments.

9.2 SAMPLE SIZE DETERMINATION

For statistical analysis purposes, sustained clinical response is defined as a reduction to a score of ≤ 2 on all symptom scores on the Modified FLU-PRO Plus questionnaire.

Based on the median time to sustained clinical response reported by CDC [122], the expected median time to response in the placebo arm will be approximately 16 days from the onset of symptoms in outpatients. With a sample size of 20 in each arm, a difference in median time to sustained clinical response of 10 days between the intervention arm and the placebo arm will be able to be detected with 81.5% statistical power with 5% Type-1 error rate. Median time to sustained clinical response will be estimated based on 21-day follow-up. With an attrition expectation of around 20%, the planned accrual is 26 patients in each arm and potentially up to 30 patients.

Patients will be randomly assigned to one of the two study arms, using a block-randomization with a block size of 4, stratified by the enrolling sites. No other stratifications will be used. Randomization block size will be kept fixed at 4 as this is a small study and making the block size random as well is not needed. An unblinded statistician will generate a randomization list.

Definition of Evaluability for Primary Objectives: The double blind, placebo controlled two-arm clinical trial is designed to enroll up to 60 patients equally randomized between the two arms of the study. An evaluable patient is defined as a patient who has received at least one dose of the intervention drug or placebo.

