Participants will be randomized to receive either TQ Formula + Standard of Care (SOC) or placebo +SOC

Administer Study Intervention

Participants will be provided with study treatment kit, with enough capsules for 14 days of treatment, 3 capsules BID.

Concomitant Medications and Adverse Events Review

Participants will be assessed for any new adverse events and any changes in concomitant medications

Patient Reported Outcomes

Participants will receive the Modified FLU-PRO Plus questionnaire to complete on a daily basis for the duration of the study, from randomization to final study visit (Day 21).

Subsequent Study Visits (Including Day 21 Final Visit)

Concomitant Medications and Adverse Events Review

Participants will be assessed for any new adverse events and any changes in concomitant medications at each study visit

Physical Exam

A complete physical exam will be performed by the investigator or appropriately qualified designee and documented in the source and in the eCRF at Day 7 and Day 14. A complete physical examination, performed at screening and other specified visits, should include an evaluation of the head, eyes, ears, nose, and throat, and the cardiovascular, dermatologic, respiratory, gastrointestinal, and neurologic systems. Any abnormality identified at baseline should be recorded in the patient's medical records. Limited, symptom-directed physical examinations should be performed at specified postbaseline visits and as clinically indicated. Changes from baseline abnormalities should be recorded in patient notes. New or worsened clinically significant abnormalities should be recorded as adverse events in the patient's medical records.

Vital Signs

Vital signs, including blood pressure (BP), temperature and heart rate will be collected and documented in source and in the eCRF at each study visit.

Serum Collection (Blood sample for immune monitoring)

Blood samples (approximately 15 ml) will be collected for immune monitoring at Day 7 and Day 14, in addition to the baseline visit.

Sample for quantitative viral load testing (RT-PCR)

Participants will have a sample taken for RT-PCR quantitative viral testing at Day 7 and again at Day 14, in addition to the baseline visit.

Laboratory Evaluations (Hematology and Serum Chemistry)

Blood samples (approximately 10ml in total) will be taken for safety laboratory evaluations (as listed in screening above) at Day 7 and 14 and as clinically indicated at any other study visits

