9.4.2 ANALYSIS OF THE PRIMARY EFFICACY ENDPOINT(S)

The primary endpoint of this clinical trial is the estimate of the median time to sustained clinical response for the treatment and placebo arms. Kaplan-Meier method will be used to estimate the time to sustained clinical response distribution and log-rank test will be utilized to compare the time to sustained clinical response distributions between the two study arms. Events will be defined as cases that attain clinical response while on the follow-up window and time to event will be calculated as the days from symptom onset to the resolution of symptoms to zero based on the Modified FLU-PRO Plus questionnaire. Patients who do not attain to clinical response while on the follow-up window will be censored on Day-21 or on the day they are off study before Day-21 due to other reasons. Although all analyses will be conducted based on the intent-to-treat context, sensitivity analyses based on the adherence to the protocol regimen will also be carried out for the primary as well as secondary objectives.

When appropriate, Last-Value-Carried-Forward (LVCF) imputation approach will be utilized for the missing values. As this is a small study that has a short span of enrollment and treatment windows, we do not anticipate excessive missing values; however, missingness structure will still be analyzed as to whether or not the missingness is Missing Completely at Random (MCAR), or Missing at Random (MAR), or Not-Missing at Random (NMAR). In the even of MCAR and MAR, sensitivity analyses will be carried out by using Multiple Imputation (MI) techniques.

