# BOSS-Covid-19 Study (BOSS-001)

1. To evaluate if treatment with 3 g TQ Formula (500 mg per capsule, 3 capsules BID) given orally on outpatient basis can significantly reduce median time to sustained clinical response compared to placebo in participants with COVID-19 infection treated in the outpatient setting. Sustained clinical response is defined as a reduction of scores to </= 2 on all symptoms of the Modified FLU-PRO Plus and should be remaining </= 2 for at least three days.
2. To evaluate the safety and tolerability of TQ Formula (500 mg oral capsule, 3 capsules BID) when given to participants with COVID-19 infection

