# BOSS-Covid-19 Study (BOSS-001)

## 5.3.2 Primary Analyses

Primary estimand-1 is defined to be the difference of median time to sustained clinical response between participants taking 3 g TQ Formula (500 mg per capsule, 3 capsules BID) and participants taking placebo regardless of whether or not they actually receive their assigned therapy (ITT) and assuming that their hospitalization and treatment discontinuation rates will be similar. Possible intercurrent events for this estimand can be, though expected to be quite rare, hospitalization (i.e., transitioning from outpatient status to inpatient status) and treatment discontinuation, both of which may lead to potential missing data or change in the primary measures. The study participants will be reminded to submit their Modified FLU-PRO Plus questionnaires even after these intercurrent events to avoid missing data as much as practically possible. Hospitalization-free, while-on-study and per-protocol treatment versions of the above estimand will also be considered within each population definitions above.

Median time to sustained clinical response for the treatment and placebo arms will be estimated using the Kaplan-Meier method and Log-rank test will be utilized to compare the time to sustained clinical response distributions between the two study arms using LIFETEST procedure in SAS Version 9.4 ® (SAS Institute, Cary, North Carolina, USA). Events will be defined as cases that attain sustained clinical response while on study and time to event will be calculated as the days from the date of symptoms onset to the date that all symptoms are below Level-2 ('A little bit') on the Modified FLU-PRO Plus questionnaire. Patients who do not attain to clinical response while on study will be censored on Day-21 or on the day they are off study before Day-21 due to other reasons.

Although all analyses will be conducted based on the intent-to-treat principle, sensitivity analyses based on the adherence to the protocol regimen will also be carried out for the primary as well as secondary objectives. Sensitivity analyses will also include hospitalization-free, while-on-study, and per-protocol treatment cohorts as described above.

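### The protocol gives 'sustained' clinical response no duration, the SAP requires three days, and the analysis sections add two more thresholds: the primary endpoint needs one definition

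*Protocol*

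**What the plan says.** **Definition.** Protocol 9.2: "For statistical analysis purposes, sustained clinical response is defined as a reduction to a score of" 2 or less on all symptom scores. The objective, endpoint and hypothesis statements in Protocol 1.1, 3, 4.1 and 9.1 use the same threshold, and none gives a minimum number of days. SAP 3.2, 3.6 and 4.1.1 keep the threshold and add persistence; in SAP 3.6 the scores "should be remaining </= 2 for at least three days". SAP 3.2 dates the event to the first day on which all items are at 2 or less.

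**Analysis text.** Protocol 9.4.2: "Events will be defined as cases that attain clinical response while on the follow-up window", with the time counted as "the days from symptom onset to the resolution of symptoms to zero based on the Modified FLU-PRO Plus questionnaire". SAP 5.3.2 makes sustained clinical response the event but dates it to "the date that all symptoms are below Level-2 ('A little bit') on the Modified FLU-PRO Plus questionnaire". It then says "Patients who do not attain to clinical response while on study will be censored on Day-21", without the word sustained.

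**Measurement.** Protocol 4.1: "Participants will receive the Modified FLU-PRO Plus questionnaire to complete on a daily basis for the duration of the study", to Day 21. SAP 7.1 fills intermittent gaps in this diary by carrying the last value forward.

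**Sizing.** In Protocol 9.2 "the expected median time to response in the placebo arm will be approximately 16 days from the onset of symptoms in outpatients". Both documents claim 81.5% power for a 10-day difference with 20 per arm.

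**Precedence.** Protocol 9.4.1 leaves analysis details to the SAP. SAP 2.2 says the SAP was prepared from protocol Version 6.0 of 17 May 2021.

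**The concern.** A first day at 2 or less and the start of a three-day run at 2 or less are different endpoints, and one set of sizing figures cannot be assumed to fit both. The protocol's word *sustained* suggests persistence, but its definition does not ask for it.

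Isolated good days are plausible on this scale. Entry needs a score of 3 or more on only two symptoms (Protocol 5.1), and response needs 2 or less on all 24 items. A participant who enters with exactly two items at 3 meets the protocol's definition if both drop one category for one evening. Good days unrelated to treatment add the same hazard to both arms, which shortens both medians and pulls the hazard ratio towards 1.

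Two written durations and three written thresholds also leave the primary endpoint open to interpretation at the analysis.

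**Working it through.** **1. Texts side by side**

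| Place | Threshold | Duration |
|---|---|---|
| Protocol 1.1, 3, 4.1, 9.1, 9.2 | all items at 2 or less | none |
| Protocol 9.4.2 | zero | none |
| SAP 3.2, 3.6, 4.1.1 | all items at 2 or less | at least three days |
| SAP 5.3.2 | below Level-2 | event sentence says sustained, censoring sentence does not |

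SAP 5.3.2 places the label 'A little bit' beside Level-2, while SAP 7.9 labels Level-2 'Somewhat' on a 0-4 scale. On that scale, below Level-2 means 1 or less.

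**2. The plan's own figure.** Inputs from Protocol 9.2 and 9.4.1: medians 16 and 6 days (16 - 10), 20 per arm, two-sided 5%. Exponential times are my assumption. The hazard ratio, placebo over active, is 6/16 = 0.375.
- Freedman, all 40 participants counted as events: z = √40 × (1 - 0.375)/(1 + 0.375) - 1.96 = 2.875 - 1.96 = 0.915, power 82.0%. This reproduces 81.5% to within a point.
- With censoring at Day 21, as planned: hazards ln2/16 = 0.0433 and ln2/6 = 0.1155 per day. Events = 20 × (2 - e^(-0.0433×21) - e^(-0.1155×21)) = 20 × (2 - 0.403 - 0.088) = 30.2. Schoenfeld: z = √(30.2/4) × |ln 0.375| - 1.96 = 0.734, power 76.9%. Simulated log-rank power is about 77%.

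**3. Adding isolated good days under the single-day rule.** Let q be the daily chance that an unrecovered participant has an isolated day with all items at 2 or less. The documents do not give q. Take it as equal in both arms and constant until recovery, with 16 v 6 days describing durable recovery counted from Day 1. Each hazard rises by -ln(1 - q). For q = 5% the increment is 0.0513, so the hazard ratio is (0.0433 + 0.0513)/(0.1155 + 0.0513) = 0.567. Expected events are 36.7, z = √(36.7/4) × 0.567 - 1.96 = -0.243, and power is 40.4%.

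| q per day | Hazard ratio | Schoenfeld, single day | Simulated, single day | Simulated, three days |
|---|---|---|---|---|
| 0 | 0.375 | 76.9% | 77% | 75% |
| 2% | 0.468 | 59.5% | 59% | 75% |
| 3% | 0.505 | 52.1% | 53% | 75% |
| 5% | 0.567 | 40.4% | 40% | 76% |
| 10% | 0.673 | 23.4% | 22% | 74% |

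The simulated columns use 8,000 trials per setting, 20 per arm and a daily diary to Day 21; a three-day run must start by Day 19. Other simulation runs gave 57-59%, 38-40% and 22-25% for the single-day rule at q = 2%, 5% and 10%. At 26 per arm without dropout, the single-day rule gives 86%, 71%, 63%, 50% and 28% down the table, and the three-day rule 84-85%. Above 10% the three-day rule also weakens: 72% at q = 15% and 68% at q = 20%, with 20 per arm.

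**4. Rate needed for a one-third loss.** Solving the Schoenfeld expression for a fall from 76.9% to 51.2% gives q = 3.1% per day. Freedman with 40 events, 82.0% to 54.7%, gives 3.0%.

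**5. Other patterns** (single-day rule, 20 per arm, q = 5%, against 77% with no isolated good days):
- good days only in the five days before recovery: 77%, no loss;
- only 30% of participants fluctuate: 65%, about 16% relative loss;
- active-arm rate 1.5 times placebo: 58%, about 25% relative loss;
- active-arm rate 16/6 = 2.67 times placebo: 86%, a gain.

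**6. Missing diary days.** Under SAP 7.1, one good day followed by two missing evenings and a later entry is filled as three good days. The SAP does not require the three days to be observed.

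**The case against.** The strongest reply is that the SAP governs analysis detail, states the three-day rule in three sections, and was written against a later protocol version. The supplied protocol describes its present as January 2021, and its eligibility text differs from the SAP's, so the mismatch may be one of versions and may already be repaired. This stands as far as it goes: under the SAP's rule the loss largely disappears. It does not settle the point, because SAP 5.3.2 itself departs from the threshold used elsewhere in the SAP.

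Three stronger readings are tempting and should be resisted.
- *Power falls by a third or more.* A reader might infer this from the lower rows of the table. The documents give no rate of isolated good days and no pattern for them. They do not say whether the 16-day median means a first good day or durable recovery; if it means a first good day, the single-day rule loses nothing. If zero in Protocol 9.4.2 governs, an isolated day at 2 or less does not date an event at all.
- *A one- or two-day responder is neither an event nor censored.* The censoring sentence in SAP 5.3.2 follows the event definition and is naturally read as its complement. The wording is loose, but the participant is not lost.
- *The definition will be chosen after seeing results.* SAP 7.7 locks the efficacy data before the statistician is unblinded. Ambiguity leaves room for such a choice, but nothing in the documents points to one.

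**Conclusion.** The conflict is established by the texts alone: no duration in the protocol's definitions, at least three days in the SAP's, and two further thresholds in the analysis sections, all under one set of sizing figures. Read literally, the protocol's definition counts one good day as a sustained response.

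The effect on power is conditional. With isolated good days equally frequent in both arms until recovery, and 16 v 6 days describing durable recovery, the single-day rule loses roughly 18 percentage points at 20 per arm if q is 2% per day and more than half the power if q is 10%. The three-day rule is almost unaffected over that range. Different patterns shrink, remove or reverse the loss, and none of it occurs if the SAP's rule is analysed. The model counts time from Day 1, whereas the plan's median runs from symptom onset; the documents give no figure to bridge the two.

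This should be corrected because it concerns the primary endpoint and costs little, not because a particular loss of power has been shown.

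**What to change.** - Use one definition in Protocol 1.1, 3, 4.1, 9.1, 9.2 and 9.4.2 and in SAP 3.2, 3.6, 4.1.1 and 5.3.2: all items at 2 or less on at least three consecutive days, with the event dated to the first of them.
- Replace zero in Protocol 9.4.2 and below Level-2 in SAP 5.3.2 with that threshold.
- Write sustained clinical response in both the event and the censoring sentences.
- Require the three days to be observed, not supplied by carry-forward under SAP 7.1.
- Censor runs that are not confirmed by Day 21.
- Restate power for this definition with Day-21 censoring: about 75-77% at 20 per arm on the exponential model, instead of 81.5%.
- If Version 6.0 already carries the three-day rule, confirm that and correct only what remains.

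The cost is wording in both documents and a revised power statement; no new data are needed. The endpoint becomes slightly harder to reach than the protocol now states, and the stated power slightly lower.
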